## 1.0 STUDY SYNOPSIS

Name of Sponsor:	Nektar Therapeutics
Name of Finished Product:	NKTR-102 for Injection
Name of Active Ingredient:	NKTR-102 (etirinotecan pegol)
Title of Study:	An Open-label, Multicenter, Extension Study of NKTR-102 in Subjects Previously Enrolled in NKTR-102 Studies
Study Period:	The estimated study duration is approximately 5 years. The duration of treatment in this study is estimated to be approximately 2 years. Subjects may continue to receive repeated cycles of study drug treatment until progression of disease, unacceptable toxicity, death, withdrawal by subject, Investigator decision, lost to follow-up, or study is terminated by the Sponsor.
Phase of Development:	Phase 2
Indication:	Solid tumors
Objectives:	
Primary Objective:
 
 
To provide access to NKTR-102 to subjects who previously received NKTR-102 in a clinical trial and are without signs of disease progression since receiving NKTR-102.
 
 
Secondary Objectives:
 
 
To evaluate the safety of continued exposure to NKTR-102.
 
To observe disease status and survival status in subjects receiving NKTR-102.
 
To evaluate the efficacy of NKTR-102 in subjects with advanced or metastatic solid tumors.
 

Endpoints:	
 
Incidence and duration of toxicities, with severity grading according to National Cancer Institute - Common Terminology Criteria for Adverse Events (NCI-CTCAE) version 4.0.
 
Tumor response per Response Evaluation Criteria in Solid Tumors (RECIST) version 1.1
 

Number of Study Sites:	Up to 100 study sites may participate in this study.
Countries:	Multi-national
Number of Subjects (planned):	Up to 150 subjects may be enrolled in this study.
Study Design:	
This is a multicenter, open-label, Phase 2 study of NKTR-102 in subjects with solid tumors who received NKTR-102 in a prior Nektar-sponsored clinical study. Following completion of NKTR-102 treatment on a prior NKTR-102 clinical study, subjects will be assessed for eligibility. The Sponsor must assess eligibility criteria prior to enrollment of all subjects.
 
Eligible subjects will continue treatment with NKTR-102 at a dose of 145 mg/m^2 or less in a q21d schedule. Subjects who previously received a dose of NKTR-102 at <145 mg/m^2 will continue at the lower dose in this study. Subjects who underwent dose reduction of NKTR-102 due to observed toxicity prior to participation in the Extension study (Protocol 11-PIR-09) will not be

re-escalated to the previous dose level upon resolution of the toxicity. Dose escalation for NKTR-102 is not permitted.

Disease assessments for tumor response and progression will be performed as per local standard of care until disease progression. Minimal disease evaluation data (best response and date of progression) will be collected within this protocol. Tumor measurements are not required; only an overall assessment of response or progression by the Investigator is required. Subjects may continue to receive repeated cycles of NKTR-102 on this protocol as long as there is evidence of disease control in the judgment of the Investigator or until there is unacceptable toxicity, death, withdrawal of consent by the subject, Investigator decision, subject non-compliance, lost to follow-up, or study is terminated by the Sponsor. After discontinuation of NKTR-102, all subjects, except those who withdraw consent from further study follow-up, are to be followed for disease status (as applicable), subsequent anti-cancer therapy, survival status, and resolution of toxicity attributable to study drug (with contact by phone, through a clinic visit, or through review of medical records approximately every 12 weeks ( $\pm 4$  weeks)).

**Concomitant Medications:**

Permitted Treatments:

- Palliative and supportive care for disease-related symptoms.
- Standard therapies for concurrent medical conditions, including antiemetic prophylaxis and early interventional antidiarrheal therapy.
- Diarrhea is an expected toxicity of NKTR-102. All subjects must receive optimal antidiarrheal therapy immediately after the FIRST episode of diarrhea or loose stool regardless of severity.
- Premedication with antihistamine and/or corticosteroid is allowed in subsequent cycles following occurrence of a self-limiting allergic/hypersensitivity reaction to a prior infusion of NKTR-102.

Prohibited Treatments:

- Any concurrent chemotherapy (other than NKTR-102), radiotherapy (with the exception of palliative radiation), biological therapy, hormonal agents used for the treatment of cancer, immunotherapy, or other systemic therapy for cancer; megestrol acetate for appetite stimulation may be used.
- Other investigational agents within 28 days prior to Day 1 of Cycle 1 or during the study.
- Investigators must monitor subjects for use of potent cytochrome P450 3A4 (CYP3A4) inducers or inhibitors, as they may induce or inhibit irinotecan or SN38 metabolism. Some of these agents are over-the-counter medications (e.g., St John's Wort); subjects must provide a complete list of all concomitant medications as part of the screening process.

**Inclusion Criteria:**

Subjects must meet the following criteria to be eligible for enrollment:

- 1) Subject or subject's legal representative must provide written informed consent
- 2) Subject is able and willing to comply with the study visit schedule and procedures

- 3) Subjects must have received prior treatment with NKTR-102 in a Nektar-sponsored study
- 4) Subjects must be without signs of disease progression since receiving NKTR-102
- 5) Women of childbearing potential must have a negative serum pregnancy test at screening and a negative urine pregnancy test at the predose visit of each cycle
- 6) Women of childbearing potential and men who agree to use adequate contraception during study participation (at least two methods of contraception, one of which includes a barrier method [male condom] by the male partner or abstinence) or a male who has undergone a vasectomy greater than 6 months prior to Cycle 1 Day 1. Appropriate contraception must be used for at least 8 months after the last dose of the study drug on this extension study
- 7) Subjects must meet requirements with respect to hematopoietic function (hemoglobin  $\geq$  8.0 g/dL or 80 g/L; absolute neutrophil count (ANC)  $\geq$   $1.5 \times 10^9$ /L; platelets  $\geq$   $75 \times 10^9$ /L).
- 8) Subjects must be able to receive the first dose of NKTR-102 in the extension study within 8 weeks after receiving their last dose of NKTR-102

**Exclusion Criteria:**

Subjects who meet any of the following criteria are ineligible for enrollment:

- 1) Subjects who have received intervening anti-cancer therapy (between their last dose of NKTR-102 and administration of the first dose of NKTR-102 in this extension study)
- 2) Subjects with 2 dose reductions of NKTR-102 and have a toxicity that requires another dose reduction
- 3) Female subjects who are pregnant or lactating, who plan to get pregnant, or who have a positive pregnancy test at screening or during participation in this study

**Test Product, dose and mode of administration:**

NKTR-102 will be administered as an intravenous (IV) infusion over approximately 90 minutes ( $\pm$  15 minutes) on Day 1 of each 21-day treatment cycle. The dose of NKTR-102 will be 145 mg/m^2 or less. Subjects who received a dose of NKTR-102 at <145 mg/m^2 will continue at the lower dose in this study. Subjects who underwent 2 dose reductions of NKTR-102 due to observed toxicity prior to participation in the Extension study will not be re-escalated to the previous dose level upon resolution of the toxicity. Dose escalation for NKTR-102 is not permitted.

**Duration of Treatment:**

Subjects will continue to receive study drug treatment until progression of disease, unacceptable toxicity, death, withdrawal by the subject, Principal Investigator decision, lost to follow-up, or study is terminated by the Sponsor.

**Reference Therapy, dose and mode of administration, batch number (if applicable):**

Not applicable

Disease Evaluation (per Standard of Care):	Tumor assessments will be performed according to local standard of care until disease progression.
Statistical Methods:	
The primary objective will be measured by capturing AEs and SAEs using the data capture tools provided for this study.
 
The primary endpoint of this study is to assess the incidence and duration of toxicities, with severity grading according to NCI-CTCAE v. 4.0.
 
The incidence and duration of AEs will be tabulated by MedDRA preferred term, system organ class, severity grading by NCI-CTCAE v. 4.0 criteria and relationship to study drug. The maximum intensity and frequency of AEs will be summarized by treatment (dose level).
 
Tumor response will be summarized by histological tumor type and tabulated using by-subject listings based on disease assessments from this protocol.

NKTR-102 Dose Modification:	NKTR-102 dose modifications are provided in Section 6.7.
Safety Monitoring:	Clinical examinations including physical examinations and vital signs. Local laboratory assessments including bone marrow, liver, and renal functions will be performed before each cycle of NKTR-102. Other laboratory assessments can be performed at the investigator's discretion.

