#### **6.5 Dosage and Administration**

Body surface area (BSA) will be determined before the start of each cycle, based on baseline height and most recent weight. Body surface area may be calculated based on institutional guidelines. NKTR-102 will be administered as an IV infusion over 90 minutes ( $\pm$  15 minutes). The recommended dose and schedule of NKTR-102 is 145 mg/m^2 q21d, with BSA capped at 2.4 m^2. Subjects who were previously receiving the 145 mg/m^2 dose will continue to receive this dose in this extension study in a q21d schedule.

Subjects originally enrolled in a clinical study in which a lower-than-recommended dose was administered (e.g., Protocol 12-102-13 in subjects with impaired liver function) or was being administered after a dose reduction will continue to receive that same dose in a q21d schedule in this study. For Protocol 12-102-13 subjects with hepatic dysfunction, as defined in that study, will continue in this extension study (Protocol 11-PIR-09) to receive the originally assigned dose from the 12-102-13 study in a q21d schedule.

Subjects originally enrolled in a clinical study in which a higher-than-recommended dose was being administered (e.g., Protocol 12-102-12 to explore the effects of NKTR-102 on cardiac function) will receive the recommended dose of NKTR-102 of 145 mg/m^2 in a q21d schedule in this extension study (Protocol 11-PIR-09).

Subjects who underwent dose reduction of NKTR-102 due to observed toxicity prior to participation in the Extension study [Protocol 11-PIR-09] will not be re-escalated to the previous dose level upon resolution of the toxicity.

Dose escalation for NKTR-102 is not permitted.

Refer to the Pharmacy Binder for further information.

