## 6.7 Dose Modifications and Delays

All adverse events (AEs) will be assessed according to the NCI-CTCAE version 4.0. In the event of multiple toxicities, dose delays and modifications should occur in accordance with the worst toxicity observed.

Specific dose modifications for NKTR-102 will be made for diarrhea, dehydration, hematological, and other non-hematological toxicities. Dose delays may be permitted between cycles.

Prior to initiation of subsequent NKTR-102 cycles, subjects must meet requirements with respect to hematopoietic function (hemoglobin  $\geq 8.0$  g/dL or 80 g/L; ANC  $\geq 1.5 \times 10^9$ /L; platelets  $\geq 75 \times 10^9$ /L). Diarrhea must be fully resolved to NCI-CTCAE Grade 0 (a return to normal bowel movement habits) for at least 7 days without supportive antidiarrheal measures prior to retreatment. Any treatment-related non-hematologic toxicities must have resolved to baseline or Grade 1.

If the subject fails to meet the criteria for re-treatment, treatment may be delayed, followed by an additional evaluation to determine feasibility of retreatment. Initiation of subsequent doses may be delayed for a maximum of 28 days to allow recovery from any toxicity to permit retreatment. Subjects whose treatment delays are  $\geq 14$  days but  $\leq 28$  days due to a drug-related toxicity must initiate their next treatment cycle with a dose reduction. Subjects who require  $> 28$  days delay due to unresolved toxicity must be withdrawn from treatment, unless, in the Investigator's opinion, continuing in the study is of benefit for the subject. In this case, the continuation of treatment must be discussed with the Medical Monitor and the reason for continuation must be approved and documented.

Subjects from Protocol 12-102-13 with impaired liver function who are entering the extension study will receive the same dose as that received in the 12-102-13 study. Investigators may choose to reduce the dose of NKTR-102 for either drug-related or non-drug related Grade 3 or higher liver dysfunction only after approval from Nektar Medical Monitor.

Supportive care may be implemented in order to treat diarrhea, nausea, vomiting, anorexia, myelosuppression, and/or other AEs. Dose delays may be implemented to permit recovery if a subject is demonstrating clinical benefit, but with repeated Grade 2 toxicities that would otherwise mandate withdrawal.

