Dose reductions may also be implemented for subjects who experience recurrent or specific severe toxicities (see [Table 4](#)). NKTR-102 doses for an individual subject may be reduced by 25 mg/m^2 based on conditions listed in [Table 4](#). Subjects should be discontinued from the study treatment if toxicity would indicate more than 2 dose reductions. Dose re-escalation for NKTR-102 is not permitted.

- For subjects entering this study at a starting dose of 145 mg/m^2: dose reductions to 120 mg/m^2, then to 95 mg/m^2 may occur based on conditions listed in [Table 4](#).
- For subjects (i.e., from Protocol 12-102-13) entering this study at a starting dose of 120 mg/m^2: dose reductions to 95 mg/m^2, then to 70 mg/m^2 may occur based on conditions listed in [Table 4](#).
- For subjects (i.e., from Protocol 12-102-13) entering this study at a starting dose of 95 mg/m^2: dose reduction to 70 mg/m^2 may occur based on conditions listed in [Table 4](#).
- For subjects (i.e., from Protocol 12-102-13) entering this study at a starting dose of 50 mg/m^2: dose reduction should be approved by Medical Monitor.
- [Table 4](#) provides instructions regarding dose modification.
- DURING A CYCLE: [Table 4](#)/Column 2 describes the recommended guidelines for management and supportive care during a cycle of therapy.
- INITIATION OF A SUBSEQUENT CYCLE: [Table 4](#)/Column 3 describes the recommended dose modifications for Day 1 in subsequent cycles of therapy. All dose modifications in a new cycle should be based on the worst toxicity observed in the previous cycle and the dose reduction will be relative to the Day 1 dose of the previous cycle.

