### 7.1 Screening

The following procedures will be performed for all potential subjects at a screening visit conducted within 28 days prior to Cycle 1 Day 1. Any procedures, as applicable, that were completed as part of the end-of-study visit for the original protocol may be used and do not need to be repeated if they were performed within 7 days of Cycle 1 Day 1 of this extension study. The maximum delay between treatment with the last dose of NKTR-102 and treatment with NKTR-102 in this study is 8 weeks.

- Informed consent by subject or subject's legal representative
- Medication history (including previous chemotherapy, radiation, treatment with biologics, OTC drugs, herbs and St. John's Wort)
- Demographics including birth date, race/ethnicity, and gender at birth
- Complete physical examination, including height and body weight and vital signs (pulse, temperature, and blood pressure)
- ECOG performance status
- Serum pregnancy test (WCBP only)
- Disease assessment with computed tomography (CT), magnetic resonance imaging (MRI) scanning, or digital photography, unless subject had disease assessment within 8 weeks prior to treatment in the Extension study
- Hematology and serum chemistry: minimally required are hemoglobin, ANC, platelets, and creatinine. Complete blood count (CBC) and other laboratory tests will be obtained at the discretion of the Investigator.
- Assessment of AEs (see Section [9.2](#) for details on AE collection from the time of the original protocol to the start of the Extension study)

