## 7.2 Treatment Days

For all cycles, safety assessments are required before each treatment cycle. All results must be available before dosing. For all cycles, Day 1 assessments may be performed up to 5 days before Day 1. The following procedures will be performed prior to each dose:

- Symptom-directed physical examination, including body weight
- ECOG performance status
- Vital signs (pulse, temperature, blood pressure)
- Hematology and serum chemistry: minimally required are hemoglobin, ANC, platelets, and creatinine. Complete blood count and other laboratory tests will be obtained at the discretion of the Investigator.
- Body surface area
- Urine pregnancy test (only for WCBP)
- Assessment of concomitant medications
- Assessment of AEs
- Diarrhea must be fully resolved to NCI-CTCAE Grade 0 (a return to normal bowel movement habits) for at least 7 days without supportive antidiarrheal measures prior to treatment. Any treatment-related non-hematologic toxicities must have resolved to baseline or Grade 1
- NKTR-102 for Injection administration

**NOTE:** Disease assessment (tumor response and progression assessments) should be performed as per local standard of care. Best response and date of progression will be collected in this protocol. Other procedures and evaluations may be performed as clinically indicated and as determined by the investigator.

All safety laboratory evaluations will be performed at a local laboratory. Each laboratory must be certified and must be listed on the Statement of Investigator Form FDA 1572.

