**17.0 APPENDICES**

**Appendix 1: Schedule of Assessments**

**Appendix 2: Cytochrome 3A4 Inhibitors**

**APPENDIX 1: SCHEDULE OF ASSESSMENTS**

Study Procedures	Screening Days -28 to -1	All Cycles a	End of Treatme nt c	Quarterly Follow-up	
		Day 1 b			
Informed Consent	X				
a Cycle length is 21 days.
 
b Any procedures that were completed as part of the end-of-study visit for the original protocol that match those procedures required during Screening may be used and do not need to be repeated if they were performed within 7 days of Cycle 1 Day 1 of this extension study. For all subsequent cycles, Day 1 assessments may be performed up to 5 days before Day 1. For all cycles, safety assessments are required before each treatment cycle. All results must be available before dosing.
 
c End-of-treatment visit to occur 30 ± 7 days after last dose of NKTR-102.
 
d There will be a complete physical exam with height and weight during Screening, symptom-directed physical exams with weight during treatment, and a complete physical exam with weight at the End-of-Treatment. Vital signs include pulse, temperature, and blood pressure. ECOG performance status will be assessed as part of the physical exam.
 
e Radiological exams or digital photography required during Screening unless subjects had disease assessment within 8 weeks prior to Cycle 1 Day 1 dosing. Disease assessments will occur during the study as per local standard of care (e.g., approximately every 6-12 weeks). CT or MRI scanning is acceptable for radiologic exams.
 
f If Grade 3 or 4 neutropenia is observed, more frequent CBC with differentials are recommended until Grade 1 or less.
 
g Minimally required: hemoglobin, ANC, platelets, and creatinine. Other tests obtained according to the Investigator’s discretion.
 
h Body surface area (BSA) will be determined before the start of each cycle, based on baseline height and most recent weight. Body surface area may be calculated based on institutional guidelines.

Eligibility Criteria	X				
Physical Examination, Vital Signs d	X	X	X		
ECOG Performance Status d	X	X	X		
Serum Pregnancy Test (for WCBP)	X				
Urine Pregnancy Test (for WCBP)		X	X		
Disease Assessment per standard of care e	X	[X]			
CBC f, g	X	X			
Serum Chemistry g	X	X			
Body Surface Area (BSA) h		X			
NKTR-102 Infusion i		X			

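### The synopsis commits to liver testing before each cycle, but the minimum set in Section 7.2 and Appendix 1 contains no liver test, so a site could omit it and still comply with the schedule

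*Protocol*

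**What the plan says.** The Safety Monitoring entry of the protocol synopsis (Section 1.0) reads: "Local laboratory assessments including bone marrow, liver, and renal functions will be performed before each cycle of NKTR-102". It leaves to the investigator only tests beyond those three organ systems, and it names no liver analyte.

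Section 7.2, which lists what is done before each dose, is narrower: "Hematology and serum chemistry: minimally required are hemoglobin, ANC, platelets, and creatinine". The rest is optional: "Complete blood count and other laboratory tests will be obtained at the discretion of the Investigator". In Appendix 1, footnote g is attached to both the CBC and the serum chemistry rows and repeats the set: "Minimally required: hemoglobin, ANC, platelets, and creatinine". Section 7.1 uses the same four analytes at screening, again with the remainder optional: "Complete blood count (CBC) and other laboratory tests will be obtained at the discretion of the Investigator".

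Two dosing rules can turn on liver function.

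- Section 6.7, in its paragraph on Protocol 12-102-13 subjects, lets the investigator reduce the dose "for either drug-related or non-drug related Grade 3 or higher liver dysfunction only after approval from Nektar Medical Monitor". Such subjects do enter. Section 6.5 says "For Protocol 12-102-13 subjects with hepatic dysfunction, as defined in that study, will continue in this extension study", and the dose-reduction list in Section 6.7 has an entry beginning "For subjects (i.e., from Protocol 12-102-13) entering this study at a starting dose of 50" mg/m², alongside entries for 120 and 95 mg/m².
- Sections 6.7 and 7.2 require treatment-related non-hematologic toxicity to be back at baseline or Grade 1 before the next dose.

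**The concern.** Sites work from the visit section and the assessment schedule, not from the synopsis. If those permit a panel without liver tests, the synopsis commitment may not be carried out, and neither a site nor a monitor can tell whether an absent liver result is a deviation.

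Two things are at stake. The first is subject safety: hepatically impaired subjects are knowingly enrolled, and a liver dysfunction visible only in the laboratory would surface at sites that test by habit and not at sites that do the minimum. The second is the data. The protocol's statistical sections make safety, as graded toxicity, the primary endpoint, and Section 2.2 says this may be the longest exposure to the drug so far. Discretionary testing makes the recorded incidence of asymptomatic liver toxicity depend partly on local practice.

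**Working it through.** This is mainly a comparison of texts. The plan gives no figure of its own to reproduce.

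**Step 1. Synopsis against the operative schedule**

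| Organ function named in synopsis | Analyte in the minimum set (7.1, 7.2, footnote g) |
|---|---|
| Bone marrow | Hemoglobin, ANC, platelets |
| Renal | Creatinine |
| Liver | None |

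Two of the three are covered and liver is not. Liver tests therefore fall among the tests left to discretion.

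**Step 2. Is there reconciling text elsewhere?** ALT and AST appear only in the abbreviation lists of the protocol and SAP. Nothing in the protocol body or the SAP text requires ALT, AST or bilirubin. Section 5.1 sets hematologic entry limits but no hepatic one. The difference lies in current text and is not explained by redaction or by an amendment log.

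**Step 3. What the dosing rules need.** Applying the Grade 3 liver provision to a laboratory-only abnormality needs a current liver value. Applying the baseline-or-Grade-1 rule to a laboratory-defined liver toxicity needs a current value and, for the baseline limb, an earlier one. This protocol requires neither. Values from the parent study may exist, but their availability is not guaranteed here.

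**Step 4. How many draws are affected.** Assume the estimated 2 years of treatment applies to each subject, with 21-day cycles and no delays.

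- Day 1 visits in 730 days: floor(729/21) + 1 = 34 + 1 = 35 per subject.
- With all 150 planned subjects: 35 × 150 = 5,250.
- Treatment has no fixed cap. Over the estimated 5-year study, floor(1,824/21) + 1 = 86 + 1 = 87 per subject, and 87 × 150 = 13,050.

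These count visits at which the two texts differ. They do not count missed tests.

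**Step 5. What the Phase 3 data bound.** Inputs are from protocol Table 2, NKTR-102 arm, N = 425, 47 patients with a discontinuation due to an adverse event, counted by primary reason.

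- Listed terms: 13 + 12 + 2 + 2 + 1 + 0 + 0 = 30, none hepatic.
- Unlisted: 47 − 30 = 17, so hepatic discontinuations were at most 17/425 = 4.0%.
- A term is listed if it affected more than 1 patient in either arm, so any single hepatic term accounts for at most 1/425 = 0.2%.
- Table 1 shows no hepatic term above 20%.

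**The case against.** The strongest reply is that the four analytes are explicitly a floor. A site can satisfy both texts by adding liver tests, and the serum chemistry row is present at screening and on every Day 1. That stands: a reader might infer that a site following the schedule would omit liver testing, but the documents support only that it could.

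Second, three operative places agree with one another and a single synopsis sentence differs, so deleting the word liver there would also remove the conflict, in a study whose primary objective is access. That is a legitimate route to consistency, but it leaves both dosing rules without a required test.

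Third, the Section 6.7 liver provision is permissive, needs Medical Monitor approval, and sits in a paragraph about one subgroup of unknown size. It does not by itself justify testing everyone. The retreatment rule, however, applies to all subjects, and so does the synopsis sentence.

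Fourth, there are safeguards. Adverse events are assessed and a symptom-directed examination is done before each dose, and further tests are allowed when clinically indicated. Section 2.1.2.3 reports no obvious correlation of toxicity or SN38 pharmacokinetics with baseline liver function. These limit the concern for symptomatic events. They do not cover an emergent abnormality that is silent: Section 9.1 asks the investigator to judge whether a laboratory finding is clinically significant, which presupposes that it was measured.

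Three further inferences should be resisted. The synopsis sentence concerns testing before each cycle and does not mention screening, so Section 7.1 does not clearly conflict with it. The 5,250 draws are not an upper limit, because treatment may exceed 2 years. And Table 2 does not bound severe hepatic events: it covers only discontinuations by primary reason, not Grade 3 or 4 events, SAEs, dose reductions or silent laboratory changes, and nothing shows that it represents hepatically impaired subjects.

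**Conclusion.** The inconsistency is real. The synopsis commits to liver function testing before each cycle, and the operative schedule allows it to be left out. The consequence is greatest for Protocol 12-102-13 subjects and for retreatment decisions after a liver toxicity.

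The size of any under-detection cannot be estimated. The documents give no rate of asymptomatic liver abnormality, no count of Protocol 12-102-13 subjects, and no information on what sites test by habit. The figure of 35 draws per subject is illustrative and rests on 2 years of undelayed treatment. The 17/425 bound limits only one kind of hepatic outcome in a different study. No harm is demonstrated. The point should be corrected because it concerns safety monitoring, the sponsor evidently intended the testing, and the remedy is cheap.

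**What to change.** In Section 7.2 and Appendix 1 footnote g, extend the minimum set to hemoglobin, ANC, platelets, creatinine, ALT, AST and total bilirubin (4 + 3 = 7 analytes), run on the serum chemistry sample already scheduled for each Day 1. Name the same tests in the synopsis.

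Making the same addition in Section 7.1 is advisable because it supplies a baseline for the retreatment rule. It is an extension, not a correction of the inconsistency.

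If the sponsor does not want testing in everyone, the narrower alternative is to require these tests for Protocol 12-102-13 subjects only and to reword the synopsis to match. That would leave the retreatment rule without a required liver test for all other subjects.

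Cost: a protocol amendment with IRB/IEC approval at up to 100 sites, and three extra local-laboratory analytes per draw, with no added visit or blood draw. Section 7.2 requires results before dosing, so a late liver result could occasionally hold a dose. The existing allowance to do Day 1 assessments up to 5 days ahead limits this.
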